## 5.4 Inclusion/Exclusion Criteria

Low back pain is defined as pain occurring between the lower posterior margin of the rib cage and the horizontal gluteal fold. Low back pain intensity will be measured using the numerical rating scale (NRS) See **Table 1** below for a complete and detailed list of inclusion and exclusion criteria, and justification/rationale for exclusion.

**Table 1:** Study Inclusion/Exclusion Criteria

Inclusion Criteria	Exclusion Criteria

 
Veterans age 18-65 years seen in VA primary care for LBP (the original target population); or (as part of expanded recruitment): Veterans age 18-65 years who otherwise have had health care for LBP since 10/1/2015, and report current back pain (Justification: adults of working age)
 
	
 
'Red flag' spine conditions (spinal cord injury, infection, malignancy, fracture) or spondyloarthropathy (Justification: red flag conditions are a distinct medical condition)*
 
Pregnancy (Justification: exclusion of potentially
 


 
Must have regular access (every day, during most hours of the day) to a computer, tablet, or smartphone with internet access at home or at work (not via a public resource such as the public library). (Justification: needed for e-Questionnaire component of data collection occurring as part of UW research processes)
 
Basic computer literacy, including the ability to navigate simple websites (Justification: needed for e-Questionnaire component of data collection occurring as part of UW research processes)
 
Having a mobile phone capable of receiving alerts using text messages (Justification: needed for e-Questionnaire component of data collection occurring as part of UW research processes)
 
Must be able to understand and read English, sufficient to provide informed consent and validly complete the study assessments. (Justification: needed for informed consent and validity of study assessments)
 
Participants must enroll in the parallel study conducted at UW prior to the 2-week run-in period, and complete run-in period requirements for e-Questionnaire completion. Run-in period requirements including (1) completing the baseline e-Questionnaire, (2) completing at least 4 of 6 e-Questionnaires in the 2-week run-in period with an adequate proportion of e-Questionnaire items completed within surveys, and (3) completing the UW informed consent requirements for the (non-VA) UW component of the study. (Justification: run-in period is needed to identify participants capable of completing study procedures, including frequent and repeated data collection)
 
	
 
vulnerable populations)
 
Prisoners or incarcerated (Justification: exclusion of potentially vulnerable populations)
 
Severe active medical comorbidities or psychiatric illness likely to be a barrier to study participation including completing frequent, serial assessments (e.g., metastatic cancer). (Justification: exclusion due to likely being unable to complete study procedures)*
 
Prior diagnoses for psychotic or major thought disorder or unstable or severe psychiatric/behavioral conditions (e.g. delirium, mania, psychosis) as identified in EHR data (CDW, Cerner, etc.)* (Justification: exclusion due to likely being unable to complete study procedures)*
 
Diagnoses indicating cognitive limitations that might limit study participation (such as dementia)*
 
Thoracolumbar spine surgery in the past 1 year
 
Other major orthopedic surgery potentially impeding normal physical activities in a material way (such as surgeries involving the hip, knee, ankle, shoulder, elbow, wrist joints) within the past 6 months, or major abdominal or chest surgery within the past 6 months.*
 
Planned major orthopedic, abdominal, or chest surgery in the next 2 months.
 

---	---

\*Evaluated partially or primarily by review of EHR data (CDW or other administrative data) to identify potential participants with back pain and without red flags or other exclusions (prior to contacting potential participants)

## 5.5 Study Evaluations

### Screening

At the time of Mode 1 and/or Mode 2 recruitment as described above, research study staff will administer the Screening Checklist (Attachment AA). The Screening Checklist is comprised of the Inclusion/Exclusion criteria stated below in Table 1. The screening checklist will also questions specific to two of the subgroups included in the expanded target population. The Screening Checklist may be completed as a paper version or entered directly into a database. Screening and informed consent will typically be conducted during the same session, for potential participants that meet study criteria and proceed on to informed consent.

### EHR data collection

Prior EHR and administrative data for study participants will be obtained from the CDW or other VA data repositories that are established after the VA's transition to the Cerner system. Participants will be informed that in this study, research staff will need to periodically look up participants' information in the electronic health record. This will be so for the duration of this study, a period that may last up to 2 years after a participant begins the study. This includes looking up such information from participants' health records after the 1-year follow-up period. If a participant decides to withdraw from this study, however, and informs the research team not to access his/her health record after that time, we will not access that participant's health record after that time. EHR reviews will be conducted to ascertain participants' status with regards to the subgroups in the expanded target population as described above (facet-mediated pain, SIJ-mediated pain, spondylolysis) and the other subgroups described below in 5.6.2.a (LSSR and LSS).

### **ActiGraph data collection**

Study participants may be provided with an ActiGraph wGT3X-BT unit at or after the time of recruitment, depending on whether an ActiGraph unit is available for use at the time of recruitment. Potential participants who do not want to wear the ActiGraph or express hesitancy about their ability to use the ActiGraph will be offered study participation without the component of wearing the ActiGraph. Thus, this paragraph pertains to those participants who wear the ActiGraph. Participants recruited by Mode 1 (in-person) recruitment will be provided an ActiGraph and a thigh strap at the time of recruitment. Otherwise, ActiGraphs will be mailed to study participants. The ActiGraph wGT3X-BT is a triaxial accelerometer that has been validated as a measure of walking in LBP and for the measurement of other types of activity when worn on the thigh (sitting, standing, lying supine, and running). The ActiGraph does **not** display step counts or activity levels, limiting participants' capacity to be influenced by this data. Participants who receive the device will wear the ActiGraph on the thigh all day except when in water. After wearing the ActiGraph for the 1st 4 weeks of follow-up, participants will mail back the unit in a prepaid delivery box that will be sent to participants in advance of the 4-week follow-up time point. Once ActiGraph units are received back, data will be downloaded from the ActiGraph using VA-approved software, and all data erased before subsequent use. According to the plan previously agreed to by the VA ISSO [name], data is downloaded first to a VA-approved external hard drive, and then transferred to the VA network. We will use existing ActiGraph algorithms for distinguishing types of activities (sitting, standing, lying supine, and running). No wireless or remote data sharing will be enabled on the ActiGraph, so no data can be transmitted in this way, safeguarding data and participants' privacy. ActiGraphs will be periodically tested for proper functioning by being worn by participant staff and the ActiGraph output examined.

**All other study evaluations as described immediately below will be conducted as part of the e-Questionnaires that are non-VA data collection. These are presented here for the sake of completeness, although their initial conduct/acquisition are not a part of the VA component of the research.** After acquisition as part of the non-VA component of this research, the data will be shared with the VA study team, and henceforth will become VA data. The baseline e-Questionnaire will be administered within 2 days of a participant completing informed consent. Scheduled e-questionnaires will be administered 3 times weekly during weeks 1-4, once a week during weeks 5-8, and twice a month from months 2-12. The exit e-Questionnaire will be administered at 1-year follow-up. Flare window e-Questionnaires are completed on an ad hoc basis during the 1-year follow-up period, and are participant-initiated (not on a set schedule)

### **Baseline e-Questionnaire**

The baseline e-Questionnaire to be administered as part of the UW (non-VA) study is provided

(Attachment Q1). Of note, only the content of the e-Questionnaires can be provided, not the actual e-Questionnaires, since they are administered electronically. Below we list some of the study measures that are included in the baseline e-Questionnaires. Other measures may be added to this list in future PRAFs. The citations provided for these measures provide detailed descriptions of the measures, including validity and reliability.

- *Roland-Morris Disability Questionnaire (RMDQ):* The RMDQ is a back pain specific functional status questionnaire adapted from the Sickness Impact. The RMDQ consists of 24 yes/no items, which represent common dysfunctions in daily activities experienced by participants with low back pain. A single unweighted score is derived by summing the 24 items, with higher scores indicating worse function with 0 (no disability) to 24 (maximum disability). The RMDQ was designed for paper administration, and is also well-suited for electronic device-based administration or telephone use.
- *Pain Numerical Rating Scale (NRS):* We will measure back pain using a 0-10 pain NRS (0=no pain and 10=worst pain imaginable) assessing average pain over the past week and pain “right now”. Numerical rating scales of pain intensity are valid, reliable, and sensitive to detecting change in pain intensity after treatment. We will also ask participants to make a second report of what they expect their NRS rating for back pain would be if they were not currently or recently taking medications for pain (analgesics).
- *PROMIS Short Form 10:* The NIH Task Force on Research Standards for Chronic Low Back Pain recommended using PROMIS Short Form items to assess the constructs of depression, anxiety, physical function, pain interference, fatigue, sleep disturbance, and satisfaction with participation in social roles.
- *Tampa Scale of Kinesiophobia (TSK):* The TSK is a 17-item scale developed to measure the fear of movement related to chronic lower back pain.
- *UW Concerns about Pain Scale 8-item SF* (previously called the UW Pain Appraisal Scale). This is a validated 8-item scale, described further at: <https://uwcorr.washington.edu/measures/uw-cap/>
- *PROMIS depression short-form (PHQ-8):* The *PROMIS depression short-forms have been previously validated*
- *The Single-item Global Measure of Depression* This single-item self-report measure of depression has been validated as compared to the Clinically Useful Depression Outcome scale, which involves 16 items assessing the DSM-IV inclusion criteria for major depressive disorder.
- *Post-traumatic stress disorder (PTSD) Checklist, civilian version (PCL-C):* The PCL is a standardized self-report rating scale for PTSD comprising 17 items that correspond to the key symptoms of PTSD.

- *Single-item stress question (SISQ)* The SISQ has been shown to have content, criterion, and construct validity in comparison to comprehensive measures of stress, well-being, psychological symptoms, and sleep disturbances.
- *Chronic Pain Acceptance Questionnaire*: This 20-item scale was designed to measure acceptance of pain. The acceptance of chronic pain is thought to reduce unsuccessful attempts to avoid or control pain and thus focus on engaging in valued activities and pursuing meaningful goals.
- *UW Pain Self-efficacy Questionnaire*: This questionnaire was developed to assess the confidence people with ongoing pain have in performing activities while in pain (<https://uwcorr.washington.edu/measures/uw-prse/>).
- *Medications*: Patients will report medications they have taken for pain in the past 24 hours.

Other variables to be included in the baseline e-Questionnaire include: low back pain history characteristics, work-related factors (receiving disability or compensation, or planned applications, hours/days off work at baseline, job satisfaction ratings, physical demands at work), smoking and vaping history, and questions with regards to current typical number of alcoholic beverages consumed per week and cannabinoid use.

### Scheduled e-Questionnaires

We have now provided an updated version of the Scheduled e-Questionnaire content (Attachment Q2-Scheduled e-Questionnaire). As mentioned above, this e-Questionnaire is part of the UW (non-VA) study processes. Only the *content* of the e-Questionnaire can be provided, not the actual e-Questionnaire, since it is an electronic questionnaire. Variables included in both Scheduled and Flare Window e-Questionnaires include several of the measures listed immediately above under "Baseline e-Questionnaire", such as: numerical rating scales of low back pain intensity, analgesic use, the 2-item version of the Coping Strategies Questionnaire, the 2-item version of the TSK, the 1-item global measure severity of depression, the 2-item version of the PCL-C scale, the single-item stress question (SISQ), hours of lost work, other variables related to work quality/quantity, recent cigarette smoking, vaping history, number of alcoholic beverages consumed and cannabinoid use.

### Flare Window e-Questionnaires

The flare window e-Questionnaire material **includes the same content as the Scheduled e-Questionnaire content** (Attachment B-Scheduled e-Questionnaire), but the wording of items are slightly different, to indicate the reference time period occurring prior to flare onset (instead of prior to the expected Scheduled e-Questionnaire start time). This e-Questionnaire (to be administered as part of the non-VA study processes) is submitted to the VAPSHCS IRB currently (see Attachment Q3). Only the content of the e-Questionnaire can be provided, not the actual e-Questionnaire, since it is administered electronically.

### Exit e-Questionnaire

*The exit e-Questionnaire to be administered as part of the non-VA study processes will be provided to the VAPSHCS IRB at a future PRAF. The exit e-Questionnaire materials include many of the same measures as contained in the baseline e-Questionnaire, but omit some measures that need only be assessed at baseline (and not at final follow-up). The exit e-Questionnaire will also include measures of global perceived improvement and satisfaction, which were not included on the baseline e-Questionnaire.*

### **Brief Telephone-based Exit Survey**

For participants who have been unable to complete the Exit e-Questionnaire, we will offer a brief telephone-based Exit Survey. The brief telephone-based Exit Survey is limited to 25 questions, 24 of which are yes/no questions, and 1 of which is a 10-point scale. Participants will already be familiar with these items from prior surveys they have completed in the study, and the telephone-based Exit Survey should take between 5-10 minutes to complete. We will make up to 2 phone contacts in which a voicemail can be left, or if a participant declines the brief telephone-based Exit Survey (whichever comes first). We provide the questions for the new telephone-based Exit Survey in Attachment ZZ. Participants completing the brief telephone-based Exit Survey will be compensated the same amount as if they had completed the full electronic Exit e-Questionnaire.

[figure not shown]
### **VA data storage.**

See Section 7.0 for further information relevant to data storage.

Part of the VA research records will be stored in paper form in a locked file cabinet (in the locked office space of the Seattle ERIC at VA Puget Sound) and part will be stored electronically. The file cabinets and computers will be locked and are housed in rooms that are locked when unoccupied. Other information will be stored electronically. All electronic data will be stored in encrypted, password-protected files on the VA secure research server with access restricted to VA research staff on this study team. Data will not be stored on any laptops or computers outside VA Puget Sound.

## **5.6 Data Analysis**

**5.6.1 Sample Size Calculations:** Of the recruitment goal of 730 Veterans, we expect that 290 Veterans (40%) will have limited data available (i.e. they will fail the run-in period, be non-compliant with e-Questionnaire data collection, be lost to follow-up, or withdraw). All data analysis will be conducted using VA data (including e-Questionnaire data that has been downloaded to the VA and has become VA data) by the biostatistical team from the Seattle ERIC listed in this human subjects application ([name], [name], [name], [name]). Key determinants of statistical power for the Aim 1 case-crossover analysis include the (1) activity exposure effect size, (2) activity frequencies (expected to be 5-

25% based on a previously conducted pilot study), (3) number of case/control periods, and (4) proportion of participants who are statistically informative (with both case and control periods). Given the transient nature of flares, in our view, only activity exposures with moderate magnitude effects (ORs of 1.5-2.0) will have a meaningful impact on the population level. Informed by the characteristics of activities, flares, and missing data from our pilot, we estimated power using simulated data with 1000 replications, assuming  $\alpha=0.005$  (Bonferroni-corrected for 10 activity groups), comparing different assumptions for sample size determinants, including activity frequencies as low as 3%. A sample size of  $n=440$  yielded  $\approx 90\%$  power to detect ORs of 1.5 for activity frequencies  $\approx 10\%$ , 80% power to detect OR=1.6 at activity frequency=5%, and 80% power for OR= 1.81 given activity frequencies as low as 3% (**Figure 2**). Allowing for 40% of participants not being analyzed due to having limited data available (loss to follow-up, fail run-in period, etc.), this yielded **a planned sample size of  $n=730$  for Aim 1**. These power estimates are highly conservative, since (1) they use data from scheduled e-Questionnaires only and assume no data from *ad hoc* flare-window e-Questionnaires, and (2) they assume no information at all from the  $n=290$  with limited data. Moreover, they are based on binary activity exposures, and analyses using continuous exposures (incorporating duration and frequency) will have greater power. As a point of comparison, the previously conducted pilot study was able to detect ORs  $\geq 2.5$  and  $p$ -values  $< 0.001$  despite having  $\sim 9x$  fewer participants than the currently proposed study. For Aim 2, using the same data simulated for Aim 1, and assuming an expected mean (standard deviation) 1-year RMDQ scores of 8.8 (6.4) from a prior study, Bonferroni-corrected  $\alpha=0.005$ , activity frequencies  $\approx 20\%$ , and  $n=440$  without missing data (from  $n=730$  initially recruited), we estimated power over a range of scenarios where we varied the strength of the association between the *change* in activity frequency over the 1st 4 weeks of follow-up (for each of the 10 activity categories) and a minimum clinically important change in 1-year RMDQ of 2.5 points. We found  $\geq 80\%$  power to detect a 2.5-RMDQ-point difference at 12 months in scenarios where a 65% change in activity frequency over the 1st 4 weeks produced a 2.5-RMDQ-point difference at 12 months, and in all scenarios where the activity frequency-RMDQ relationships was *more* extreme (e.g., if a smaller % change in activity frequency produced a 2.5-RMDQ-point difference at 12 months. This confirms adequate power with **a planned sample size of  $n=730$  for Aim 2**.

**5.6.2. Analytic approach:** All analyses will be conducted at VA by members of the Seattle ERIC biostatistical team, by research staff member biostatisticians named on this protocol as above. It is expected that [name] and [name] of the Seattle ERIC will conduct all analyses involved. If needed, other members of the Seattle ERIC biostatistical team named above as study personnel may be called upon for analyses, such as [name] and [name]. Senior biostatistical oversight will be provided by [name] at UW; however, [name] will not interact directly with study data and/or PHI, and will only see results in aggregate format such as would be presented for publication to a scientific journal.

We will conduct analyses to identify patterns of missing data that may indicate whether they are ignorable. Approaches to deal with missingness will vary depending on patterns of missingness and may change completely from the initial approach specified here. If  $>5\%$  of outcome data are missing, the sample will be divided into two groups (missing vs. not missing) and fully observed variables will be examined to determine if they predict missingness on the affected outcome. Depending on this analysis, the missingness may be considered “observed at random” thus meeting some criteria for

[figure not shown]
“missing at random” assumptions. Multiple imputation procedures will then be implemented. If data missingness is not ignorable, we will use Heckman’s selectivity models or pattern-mixture models with multiple imputation to model the missingness. These methods for dealing with missing data may change based on the actual nature of the data and missingness.

We will characterize the study sample using descriptive statistics and graphical techniques such as frequencies, means, medians, histograms and box plots. Quantitative variables (e.g., ActiGraph data) will be transformed as needed (e.g., log transformations for positively skewed long-tailed distributions, or conversion to categorical variables based on clinical rationale or distribution). All analytic approaches as stated below are preliminary plans, and may change depending on developments in the field, new statistical innovations, and the nature of the data at hand.

**5.6.2 a. Aim 1 analyses:** We will examine associations between activity group exposures and the participant-reported flares outcome in conditional logistic regression models, using data from all scheduled and flare window e-Questionnaires over 1- year. There will be one model for each of the 10 primary activity categories. Models will include activity categories as time-varying predictors as in **equation 1**, where  $Y$  is the outcome (flare vs. no flare),  $x$  is the activity

exposure (yes vs. no), and  $C$  represents potential time-varying confounders (psychological factors, other activities). The letter  $i$  indicates the  $i^{\text{th}}$  individual ( $i = 1, 2, \dots, n$ ),  $j$  indicates the  $j^{\text{th}}$  time of follow-up ( $j = 1, 2, \dots, n_i$ ) and  $x_{i(j-1)}$  indicates an activity that was performed in the exposure window prior to the  $j^{\text{th}}$  time (either the start of the control window [scheduled e-Questionnaire] or time of flare onset [flare window e-Questionnaire]). As previously noted, the survey methods are such that activity exposure and flare outcome are inherently time-lagged, with exposure preceding outcome.  $\beta_w$  represents the association of activity  $x$  with flare outcome  $Y$  within individuals (the ‘within-individual effect’), or the expected odds of a flare with change in the activity exposure for a given individual. These analyses will yield odds ratios (OR) and 95% confidence intervals for within-individual ‘effects’ of activity triggers on an LBP flare. The initial analytic approach (**Figure 3**) will examine the association between binary activity exposure and binary flare outcome, with explicit adjustment for pain NRS and number of prior flares measured at time= $j-1$ , and time-variant confounders selected based on conceptual importance; *by design*, the case-crossover method uses each person as their own control, accounting for known and unknown confounds that are fixed or relatively stable over time (i.e., age, sex, sociodemographics, medical and LBP history, work-related factors, and underlying psychological predispositions). We will use a Bonferroni-corrected threshold of  $p=0.005$  for each

$$\log \left[ \frac{Pr(Y_{ij} = 1)}{1 - Pr(Y_{ij} = 1)} \right] = \beta_{0i} + \beta_w x_{i(j-1)} + \gamma C_{i(j-1)}, i = 1, 2, \dots, n; j = 1, 2, \dots, n_i \quad (1)$$

[figure not shown]

\*Analysis includes all scheduled and flare window e-Surveys. Activity exposures over prior 24-hr and 2-hr effect periods, and current flare status, are inherently time-lagged.

primary activity-

flare comparison to account for 10 statistical comparisons (one for each of the 10 activity categories). We will further examine for activity-flare associations after accounting for important relationships based on theory and clinical knowledge, including the following: dose-response relationships; work- specific activity-flare associations; multivariate analyses including other potential confounders (other time-varying activities, depression, PTSD, stress, catastrophizing); potential moderators; different effect-periods of activity exposures (i.e., 24 vs. 2 hours); possible biases (e.g., conscious activity avoidance and carry-over effects); and clinical subgroup analyses (lumbosacral radicular syndrome [LSRS] symptomatic lumbar spinal stenosis [SLSS] diagnosed by a specialist, ascertained by chart review). We will also conduct similar subgroup analyses as secondary analyses, targeting the expanded target population subgroups described above (facet-mediated pain, SIJ-mediated pain, spondylolysis, ascertained by EHR review). We will analyze the reliability and accuracy of these subgroups. Of note, the primary analysis of walking, standing, and sitting will use the ActiGraph data (which are only obtained for the 1st 4 weeks of follow-up); secondary analyses will use the self- reported data for these 3 groups over the entire 1-year follow-up, and will also examine the association between ActiGraph and self-reported data. After these analyses using the binary flare outcome, we will use an analogous approach to examine relationships between activity categories and the secondary (continuous) outcome of NRS LBP intensity, with linear mixed-effects regression. These analyses account for potential biases that might be introduced by participant self-identification of flare status; if no such bias exists, we would expect the direction of effects to be similar to those obtained in the initial analysis of flares.

**5.6.2b. Aim 2 analyses:** We will examine associations between the frequency of activity during scheduled e-Questionnaires (% of periods during which each of the 10 primary activity categories were reported over the 1st 4 weeks of follow-up), and the outcome of long-term LBP-related functional limitations at 12 months as reflected by the RMDQ, using a Bonferroni-corrected threshold of p=0.005 (**Figure 4**). Activity over the 1st 4 weeks is the exposure of interest for the Aim 2 analysis because activity restriction is most expected early in an episode of LBP, and because of our previously-stated reasoning that early changes in activity may be particularly important in determining long-term/overall activity-function relationships. The percentage of periods with each activity category over the 1st 4 weeks will be calculated from self-reported activity information and ActiGraph output. The main multivariate model for each activity category will explicitly adjust for a range of potential confounders based on prior knowledge and conceptual rationale, including baseline RMDQ score, and all psychological predictors and other baseline covariates. We will then conduct secondary analyses analogous to that done for Aim 1 to examine activity-1-year-RMDQ associations after accounting for important relationships based on theory and prior knowledge: potential moderation by baseline employment status, compensation status, or job satisfaction; potential moderation by analgesic use over the first 4 weeks of follow-up; sensitivity analyses contrasting associations with cumulative activity exposure early (weeks 1-2) vs. late (weeks 3-4 or weeks 5-8).

during follow-up; and clinical subgroup analyses (LSRS and SLSS subgroups). We will use the same approach for the secondary outcomes of LBP intensity, lost work productivity, quality of life, and analgesic use at 1-years.

Analyses for Aims 1 and 2 will use VA administrative data to weight the sample of participants back to represent the target population of Veterans with back pain (including those who did not respond to the study).

**5.6.3. Interpretation:** Aims 1 and 2 will yield tables of risk estimates for (1) the *short-term effects* of the 10 specific activity categories on flares and (2) the *long-term effects* of such activities on functional recovery as reflected by the 1-year RMDQ score. We expect that different activities will have different patterns of short-term vs. long-term effects. In instances where short-term and long-term effects are in the same direction, potential implications for activity recommendations may be straightforward. For example, if heavy lifting confers both greater short-term risk of pain flares *and* greater long-term risk of functional limitations at 1-year follow-up, the clinical implication may be that lifting should be avoided for those with LBP. In some instances where the short-term vs. long-term effects of activities differ, however, implications may depend on personal priorities and preferences. For example, if walking increases the short-term risk of a flare but has no effect on functional recovery at 1 year, the decision of whether or not to walk during a new LBP episode might be guided by a patient's preferences. In other instances where the short-term vs. long-term effects of activities differ in direction, the latter may take priority (i.e., if walking improves functional recovery at 1 year, but causes a small magnitude increase in pain flares, walking should likely be encouraged).

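### The observed-data check in section 5.6.2 cannot show whether missingness is ignorable, so the plan has no criterion that reliably triggers its not-ignorable analysis of 1-year RMDQ

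*Combined protocol and SAP*

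**What the plan says.** Section 5.6.2 (Analytic approach) opens its missing-data paragraph with the aim: "We will conduct analyses to identify patterns of missing data that may indicate whether they are ignorable". One check is then described. If more than 5% of outcome data are missing, participants with and without the outcome are compared, and "fully observed variables will be examined to determine if they predict missingness on the affected outcome". The consequence follows directly: "Depending on this analysis, the missingness may be considered" observed at random, which the plan says satisfies some of the missing-at-random criteria. Then: "Multiple imputation procedures will then be implemented".

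The other branch reads: "If data missingness is not ignorable, we will use Heckman’s selectivity models or pattern-mixture models with multiple imputation". No further test, threshold or criterion for not ignorable appears in the documents. The same section says the missing-data methods may change with the data.

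On the expected amount, section 5.6.1 says "we expect that 290 Veterans (40%) will have limited data available" and lists run-in failure, poor e-Questionnaire compliance, loss to follow-up and withdrawal as the reasons.

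**The concern.** Ignorability asks whether missingness depends on the unobserved outcome after conditioning on what was observed. Comparing missing and non-missing participants on observed variables separates missing completely at random from missingness related to observed data. It cannot separate missing at random from missing not at random, so its result cannot choose between the two branches in section 5.6.2.

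Aim 2 is most exposed. It has a single outcome time point (RMDQ at 12 months), and its target is the association between activity frequency in weeks 1-4 and that score. People who are doing badly, or who have recovered, may stop answering for reasons that the observed variables do not fully capture. If the comparison is then read as support for missing at random, the Aim 2 table would carry imputed results with nothing to show how far they depend on that assumption.

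**Working it through.** **1. The plan's own figures.** 290/730 = 39.7%, stated as 40%, and 730 - 290 = 440. Inflating 440 for 40% loss gives 440/(1 - 0.40) = 734, against the stated 730. These agree. They describe participants with limited data for any reason, not missing 1-year RMDQ.

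**2. Does the check track the bias?** Inputs from section 5.6.1: n = 440, 1-year RMDQ mean 8.8, SD 6.4. Assumed, because the documents do not give them: baseline to 1-year correlation 0.6; log-odds of missingness 0.8 per SD of its driver; base missing rate 20% or 40%; no true activity effect. The check is a logistic regression of missingness on baseline RMDQ and activity, tested at 5%. The analysis is the missing-at-random regression on completers. There were 1,000 replicates per row; each cell shows the 20% result, then the 40% result.

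| Missingness depends on | Check significant | Bias in mean RMDQ | Bias in activity slope (points per SD) |
|---|---|---|---|
| Nothing | 5.1%, 4.5% | 0.00, 0.00 | -0.01, 0.00 |
| Baseline RMDQ | 100%, 100% | 0.00, 0.00 | 0.00, 0.01 |
| Total 1-year RMDQ | 94.5%, 98.4% | -0.69, -1.24 | 0.01, 0.00 |
| Unseen part of 1-year RMDQ only | 3.9%, 5.5% | -0.84, -1.48 | 0.01, 0.00 |
| Unseen part, in opposite directions at high and low activity | 5.4%, 5.0% | 0.01, 0.00 | -0.80, -1.32 |

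Rows 2 and 3 look alike to the check, but only row 3 is biased. Rows 1, 4 and 5 also look alike, and rows 4 and 5 are biased. Reading a significant result as not ignorable instead does not help: the not-ignorable models would then run in row 2, where they are not needed, and usually be missed in rows 4 and 5. Row 5 is an extreme construction, included because it biases the quantity Aim 2 estimates.

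**3. Effect on a real activity association.** Take the section 5.6.1 scenario of 2.5 RMDQ points per 65% change in activity frequency, with the same assumed correlation and with log-odds of dropout 0.8 per SD of 1-year RMDQ.

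- Dropout depends on RMDQ only: the estimate falls to 2.42, 2.37 and 2.32 at base missing rates of 10%, 20% and 40%. Against 2.5 the losses are 0.08/2.5 = 3%, 0.13/2.5 = 5% and 0.18/2.5 = 7% (up to 8% against the simulated full-data value). At log-odds 0.4 the loss is about 1-2%.
- Dropout also rises with activity (assumed log-odds 0.4 per SD): the loss is about 12% at a 10% base rate, rising to roughly 35% at 40%. The upper end moves with the assumed spread of activity frequency, which the documents do not give.

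In points, 3-8% of 2.5 is 0.08 to 0.2, and 12-35% of 2.5 is 0.3 to about 0.9.

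**4. What a delta analysis would show.** If the missing participants' RMDQ is shifted by d, the overall mean moves by (missing fraction) x d. For d = 2.5 this is 0.25 points at 10% missing, 0.5 at 20% and 1.0 at 40%. A contrast between high- and low-activity groups with missing fractions m1 and m0 moves by m1·d1 - m0·d0. With equal fractions and a common shift that is zero. With 20% missing in both groups and shifts of +2.5 and 0, it is 0.20 x 2.5 = 0.5 points. A common shift alone would therefore test the mean but hardly test Aim 2's association.

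**The case against.** The wording in section 5.6.2 is tentative: patterns may indicate ignorability, only some criteria are said to be met, and the approach may change completely. The sentence on Heckman and pattern-mixture models is not tied to a particular result of the comparison. A reader might infer that the not-ignorable analysis would never run. The documents do not support that: the branch has no usable trigger, but it is not closed. Nor do they support any fixed rate at which the plan would mislabel missingness, because they give no test, significance level or mapping from result to label. The detection rates above belong to an assumed version of the check.

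A reader might also take 40% as the missing rate for 1-year RMDQ. It is not. It includes run-in failures, and section 5.4 makes passing the run-in an inclusion criterion. Section 5.5 adds a telephone exit survey with 24 yes/no items and one 10-point scale; since the RMDQ has 24 yes/no items, this appears to recover the Aim 2 outcome directly and should lower the rate. The 40% results are therefore toward the upper end.

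The Abstract and section 5.1 promise sensitivity analyses of important assumptions. That counts for something, but missing data are not named. The weighting in sections 5.3 and 5.6.2b addresses non-response to recruitment, not a missing exit score among enrolled participants.

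Finally, bias in mean RMDQ is not what Aim 2 estimates, and dropout driven by RMDQ alone costs the activity effect little. Both points are correct and limit the size. They do not make the check able to answer the question it is asked.

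**Conclusion.** The point holds as a fault in the decision rule. That observed data cannot establish ignorability is a matter of logic and needs no simulation. Following section 5.6.2 as written can leave Aim 2 on missing-at-random imputation with no not-ignorable analysis beside it.

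The consequence may be small or material. The 3-8% and roughly 12-35% losses rest on the assumed correlation of 0.6, the assumed dropout strengths, the spread of activity frequency, and a missing rate that the documents do not state. A loss of around a third should not be read as the expected result: it needs both a high missing rate and dropout that rises with activity as well as with RMDQ. The change should be made before analysis, but the point does not show that the Aim 2 estimate will be seriously wrong.

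**What to change.** Remove the test-then-choose rule from section 5.6.2 and state in advance:

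- **Main analysis of 1-year RMDQ:** multiple imputation under missing at random among participants who pass the run-in, with baseline RMDQ, serial pain NRS, flare reports and e-Questionnaire completion as auxiliary variables.
- **Sensitivity analysis, always reported:** delta-adjusted pattern-mixture imputation over a fixed range, for example -2.5 to +2.5 RMDQ points (the important change used in section 5.6.1), including shifts that differ by activity level, whatever the observed-data comparison shows.
- **Observed-data comparison:** keep it as description and to help choose auxiliary variables, not as a test of ignorability.

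The plan already names pattern-mixture models with multiple imputation, and the variables are already collected. No new data or change in sample size is needed. The cost is SAP wording, a few extra imputation runs and possibly a less certain conclusion for some activities. The exact range is a judgement; what matters is that it is set before the outcome data are examined.
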